## 13.0 BIO-STATISTICAL CONSIDERATIONS

### Power and Sample Size

Required sample size was derived for the outcomes of Aim 1. Power analysis using traditional assumptions of the repeated measures ANOVA model suggest that as few as 174 couples would be necessary to detect a small effect ( $d=.20$ ) between groups over time, an effect smaller than the observed effect on affectionate behavior in spouses/partners in our previous work[40]. However, these traditional power calculations are known to be optimistic. While there are good power formulae for MLM clustered designs and repeated measures designs, as yet there is no specific formula for calculating power for dyadic analyses. Using a formula provided by Raudenbush and Bryk[104, 105] for individual repeated measures and estimates from our previous dyadic models, we calculate a sample of 264 couples measured 4 times over a 12-month period has a power of 0.80 to detect a moderate effect ( $d=.40$ ) on change over time. As dyad models using MLM control for interdependence between members of the couple, power is increased over an individual model. We, therefore, believe this to be a more conservative estimate of power. Further attempts to increase power and reduce Type I error will be to use the omnibus hypothesis-testing procedure in the HLM program. Another rule-of-thumb is to require a minimum number of subjects per parameter estimated. Even in the most complicated model, the proposed sample of 264 couples would exceed the minimum standard of 5-10 subjects per parameter estimated.[106] No universal approach has been adopted for sample size considerations in GMM and this will be used in an exploratory aim; however, our n-to-items ratio exceeds sample size recommendations for related approaches (10-20:1).[107] In sum, the proposed sample size of 264 couples is on par with our previous trials and will allow us to detect clinically meaningful change and address study aims. To insulate the sample size against an estimated attrition of 10% across the study period, 294 couples will be randomized. The attrition estimate is more conservative than our prior trial of *Exercising Together* where no couples in the exercise program dropped out and the drop out in our current GET FIT trial that average 6% for a 6-month intervention. Couples will be enrolled into 10 waves (a new wave begins every 3-4 months) of 9-10 couples to maintain reasonable class sizes and make efficient use of testing resources. We will recruit approximately even numbers of couples coping with each type of cancer (N=98 per disease site) and stratify by cancer type at randomization.

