Aim 1: Determine the efficacy of partnered strength training on relationship quality (intimacy, communication and incongruence). A longitudinal multivariate-outcomes dyad model will be used to directly examine couple trajectories in intimacy (emotional & physical) and communication over time. This is a multi-level model where responses from the survivor and spouse/partner are modeled simultaneously to control for the interdependent nature of the data and autocorrelation among repeated assessments. These models have been described and used extensively by Co-PI [name].[22, 111-113] The Level 1 model has four coefficients representing intercepts (baseline assessments) and slopes (rates of change) for survivors and spouses/partners that become outcome variables in a Level 2 model. Models with linear and quadratic change across time will be compared to determine best fit to the data. Aim 1 will be addressed with Level-2 models that include dummy variables to directly examine the effects of the partnered intervention vs. supervised individual (dummy 1) and unsupervised individual (dummy 2) exercise groups on individual level changes (controlling for couple effects) in intimacy and communication across time. A significant group coefficient on the slopes at level 2 and significantly better fitting model (evidenced by deviance statistic) will indicate the rate of change across time is different depending on a treatment group (i.e., interaction effect). We will also explore the efficacy of *Exercising Together* on incongruence (regarding survivor pain & fatigue) in couples. Univariate-outcomes models will be used to generate Empirical Bayes estimates of the gap between survivor and spouse/partner over time for each symptom measure. This comprehensive approach to estimating incongruence has been described elsewhere[114-116] and successfully used by this team.[55, 63, 113, 117, 118] The effect of *Exercising Together* on incongruence will be directly tested (similar to above model) by a significant coefficient for one of the two GROUP variables on the slope parameter and significantly better fitting model.

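### The power section calls 0.80 conservative because both partners are modelled together, but joint modelling gives no gain for the partner-specific slope coefficients that Aim 1 tests

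*Combined protocol and SAP*

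**What the plan says.** **Power.** Section 13.0, Power and Sample Size, reports "we calculate a sample of 264 couples measured 4 times over a 12-month period has a power of 0.80 to detect" a moderate effect, d = 0.40, on change over time. The formula is described as one "for individual repeated measures and estimates from our previous dyadic models". The section acknowledges that no specific formula exists for dyadic power. It then says "As dyad models using MLM control for interdependence between members of the couple, power is increased over an individual model" and concludes "We, therefore, believe this to be a more conservative estimate of power". No calculation accompanies the claimed gain. The next sentence adds a separate device: "Further attempts to increase power and reduce Type I error will be to use the omnibus hypothesis-testing procedure in the HLM program".

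**Test.** Section 13.0, Analysis Plan, Aim 1, gives each partner an intercept and a slope at Level 1. Two arm dummies enter at Level 2 to examine effects "on individual level changes (controlling for couple effects". An effect is declared when a group coefficient on the slopes is significant and the model also fits better by the deviance statistic.

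**Design.** Couples, not individuals, are randomized (section 8.0). Both members complete all measures at 0, 3, 6 and 12 months (section 3.0, Measures and Data Collection).

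**The concern.** The power section infers extra power from the correlation between partners. In the Aim 1 model, both partners' slope equations contain the same predictors: the couple's arm and the common visit times. In that situation, estimating two equations together does not sharpen either one, so the correlation cannot provide the margin claimed.

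What is at stake is how the main power figure is read. The two sentences tell the reader that true power for Aim 1 exceeds 0.80. If the gain is absent for the coefficients actually tested, 0.80 has to stand on its own inputs, and those are not reported.

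**Working it through.** **Inputs from the plan.** 264 couples; 3 arms with even allocation, so 264/3 = 88 per arm; visits at 0, 3, 6 and 12 months; d = 0.40; 10% attrition.

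**Assumed, because the plan does not give them.** Alpha 0.05 two-sided; d standardised on the SD of true slopes; slope reliability (true slope variance divided by variance of the estimated slope) up to 1; variance components as stated below.

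**1. The plan's own figures.** 264/(1 − 0.10) = 293.3, so 294 reproduces. For the 0.80, use

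power = Φ( d × √(reliability × n1·n2/(n1+n2)) − 1.96 ).

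| Comparison | Power at reliability 1 | Reliability needed for 0.80 |
|---|---|---|
| 88 v 88 | Φ(0.40 × √44 − 1.96) = Φ(0.693) = 0.756 | (1.960 + 0.842)² / (44 × 0.16) = 7.849/7.04 = 1.11, impossible |
| 88 v 176 | Φ(0.40 × √58.67 − 1.96) = 0.865 | 7.849/9.387 = 0.836 |
| 132 v 132 | Φ(0.40 × √66 − 1.96) = 0.901 | 7.849/10.56 = 0.743 |

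One-sided, 88 v 88 gives 0.843. A 2-df test across the three arms, with both comparators 0.40 below the experimental arm, gives 0.784 to 0.789. At reliability 0.8, 88 v 88 two-sided gives Φ(0.40 × √(0.8 × 44) − 1.96) = Φ(0.413) = 0.66. The 0.80 can thus be neither confirmed nor refuted: some contrasts and reliabilities reach it, and the two-sided pairwise contrast does not under these assumptions.

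**2. Why the partner correlation drops out.** Take random intercepts and slopes, with residuals independent across visits but possibly correlated between partners at the same visit. With complete data, each couple reduces to four numbers: an intercept and a slope for each partner. Each is regressed on the same three terms (constant, dummy 1, dummy 2). When all equations share the same regressors, joint generalised least squares equals equation-by-equation least squares. For the survivor slope,

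Var(arm difference) = Var(estimated survivor slope) × (1/88 + 1/88).

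No cross-partner term appears.

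**3. Numerical check.** Illustrative components, time in years: slope variance 0.4, residual variance 0.5. Visit times are 0, 0.25, 0.5 and 1, with sum of squares about the mean 1.3125 − 4 × 0.4375² = 0.5469. Estimated-slope variance = 0.4 + 0.5/0.5469 = 1.3143. SE = √(1.3143 × 2/88) = 0.17283. These components imply a low slope reliability (0.4/1.3143 = 0.30), and they are used only for the ratio. A full calculation from the 8 × 8 couple covariance matrix gave:

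| Setting | Dyad SE / individual SE |
|---|---|
| Complete data, cross-partner random-effect correlation 0 to 0.9, residual correlation 0 to 0.5 | 0.17283/0.17283 = 1.0000 throughout |
| 10% couple-level dropout | 0.9996 to 1.0000 |
| 10% single-partner dropout | 0.986 to 1.000 |
| 30% single-partner dropout | 0.951 to 1.000 |

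Other components, with unequal partner variances and a non-proportional cross-covariance, again gave 1.0000 with complete data, and 0.993 to 1.000 with 10% single-partner dropout. In simulation with partner-specific covariates, the mean SE differed by at most about 0.0002 (0.15124 v 0.15103) and power by at most 0.003.

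**4. Size in power terms.** Even the most favourable 10% dropout ratio, 0.986, would move 0.756 only to Φ(2.653/0.986 − 1.96) = 0.768.

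**5. Targets that do gain.** With equal partner variances and correlation r between the two slope estimates, the SE of the couple-average contrast is √((1 + r)/2) times the individual one: 0.71, 0.77, 0.84 and 0.89 at r = 0, 0.2, 0.4 and 0.6. With equal effects in both partners and single-partner power 0.756, the couple-average test has power 0.84 to 0.96 and a joint 2-df test of both partners 0.755 to 0.93, over r from 0.62 down to 0.

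**The case against.** **The dyad model does gain in some settings.** This stands. When one partner drops out, the other's data carry some information, and section 8.0 foresees continued collection from the remaining partner. Partner-specific age or comorbidity covariates also break the identical-predictor condition. Both effects are small here. A couple-average or joint test can gain materially, and the exploratory incongruence analysis concerns a survivor–partner gap, so it lies outside this point. It would be wrong to infer that joint modelling never helps, or that it helps for one contrast only.

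**The plan names an omnibus procedure.** It does, but without saying which coefficients are covered, and it is presented as a further step, separate from the dyadic gain. Aim 1 requires the coefficient itself to be significant as well as a better fit. An added condition cannot raise power above that of the coefficient.

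**Conservative may only mean relative to the 174-couple ANOVA calculation.** That contrast is in the section, and subjects per parameter and parity with earlier trials are cited as well. But the conclusion follows by an explicit therefore from the dyad sentence, so the dyadic gain is its stated ground.

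**Nothing in the design depends on it.** Largely true. The 0.80 comes from a one-person formula, so removing the sentences leaves 264, 294 and 0.80 as they are. A reader might infer that attrition is now uncovered. The documents do not support that, because the 10% inflation is made separately.

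**Conclusion.** For the partner-specific arm-by-slope coefficients of Aim 1, the claimed gain in power is nil with complete data (SE ratio 1.000) and negligible with 10% single-partner dropout (about 0.99 to 1.00). Calling 0.80 conservative on this ground is unsupported for that test. Exact equality rests on complete data, the same predictors for both partners, and the random intercept-and-slope structure above; it does not depend on the size of the variance components.

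A reader might go further and infer that 0.80 is wrong or the trial underpowered. The documents do not support that step: alpha, sidedness, variance components and contrast are all unstated, and several contrasts reach 0.80 at plausible reliabilities. What can be said is conditional. For one two-sided pairwise comparison at 0.05, with d on the slope SD, power is about 0.75 at best and about 0.66 at slope reliability 0.8, so that reading of 0.80 would be optimistic.

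**What to change.** In Power and Sample Size, delete the sentence claiming that the dyad model increases power and the one concluding that the estimate is conservative. In their place, give the power for the partner-specific arm-by-slope coefficient of one pairwise comparison (88 v 88 couples), with the alpha, sidedness and slope reliability used. If 0.80 refers to a different contrast, name it and give the same inputs. The plan should not simply assert that 0.80 applies to each partner-specific coefficient, since the two-sided pairwise calculation does not reach it under the assumptions above.

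A couple-average contrast could be pre-specified and powered with its assumed within-couple correlation. That is optional, not needed for the correction, and diluted if only one partner benefits.

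The cost is wording and a less favourable power statement. Sample size, randomization, data collection and the Aim 1 test are unchanged.

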
### Analysis Plan

Standard descriptive statistics/graphics will be used to check for any departures from statistical assumptions (e.g., normality, outliers, etc.).[108] We will examine dropout and patterns of missing data to determine mechanisms (MCAR, MAR, or not ignorable). In the case of data missing MCAR or MAR, model-based maximum likelihood estimation available in the MLM approach will allow unbiased parameter estimation using all available data (i.e., missing data is handled efficiently

with no loss of information). If the rate of attrition is high and missing data is not ignorable, we will continue with the planned analyses but temper our conclusions. For each aim, we will conduct intention-to-treat (ITT) and completers only analyses. ITT analyses will include all participants regardless of adherence to exercise regimen. Based on median attendance data from our prior trials, completers will be defined as participating in 50% or more of the scheduled exercise sessions. We will track medical treatment changes, cancer recurrence, and adherence to exercise. Age, comorbidities and time since diagnosis will be considered as covariates in all analyses. All analyses will be conducted in R and HLM statistical software packages (Aim 4 will be conducted using MPlus v7.2).

Aim 1: Determine the efficacy of partnered strength training on relationship quality (intimacy, communication and incongruence). A longitudinal multivariate-outcomes dyad model will be used to directly examine couple trajectories in intimacy (emotional & physical) and communication over time. This is a multi-level model where responses from the survivor and spouse/partner are modeled simultaneously to control for the interdependent nature of the data and autocorrelation among repeated assessments. These models have been described and used extensively by Co-PI [name].[22, 111-113] The Level 1 model has four coefficients representing intercepts (baseline assessments) and slopes (rates of change) for survivors and spouses/partners that become outcome variables in a Level 2 model. Models with linear and quadratic change across time will be compared to determine best fit to the data. Aim 1 will be addressed with Level-2 models that include dummy variables to directly examine the effects of the partnered intervention vs. supervised individual (dummy 1) and unsupervised individual (dummy 2) exercise groups on individual level changes (controlling for couple effects) in intimacy and communication across time. A significant group coefficient on the slopes at level 2 and significantly better fitting model (evidenced by deviance statistic) will indicate the rate of change across time is different depending on a treatment group (i.e., interaction effect). We will also explore the efficacy of *Exercising Together* on incongruence (regarding survivor pain & fatigue) in couples. Univariate-outcomes models will be used to generate Empirical Bayes estimates of the gap between survivor and spouse/partner over time for each symptom measure. This comprehensive approach to estimating incongruence has been described elsewhere[114-116] and successfully used by this team.[55, 63, 113, 117, 118] The effect of *Exercising Together* on incongruence will be directly tested (similar to above model) by a significant coefficient for one of the two GROUP variables on the slope parameter and significantly better fitting model.

Aims 2: Determine the efficacy of partnered strength training on physical and mental health. Separate longitudinal multivariate-outcomes models will be used to directly examine the effect of partnered strength training in couples on each physical (body composition, lipids, insulin resistance, blood pressure, inflammation, and physical function) and mental health outcome (anxiety, depressive symptoms, fear of recurrence) as described above under Aim 1.

Aim 3: Determine the persistence of Exercising Together. Sustained effects will be tested by comparing linear and quadratic trajectories across time (as discussed above). We will also separately estimate and directly compare the intervention effects between the intervention (baseline to 6 months) and follow-up (6 months to 6 months after end of intervention) periods.

Aim 4: Exploratory analyses: Patterns and predictors of types of couples who benefit the most. GMM identifies distinct patterns of change that vary around different means, have unique variance and homogenous within-trajectory growth. Based on conditional probabilities, cases are assigned to the “most likely class” or pattern of change over time (e.g., couples who benefit/improve most from the intervention). Couple-level estimates from Aims above will be integrated into progressive GMM to determine if there are distinct and naturally-occurring patterns of change in outcomes over time with the dyad as the unit of analysis. Survivor-, spouse/partner- and couple-level

determinants of fitting one pattern of change over the other(s) will be modeled using logistic, multinomial or ordinal regression as appropriate. This integrated multilevel and mixture modeling approach has been used previously by this team,[118] as it allows us to identify types of dyads and differentiate them based on individual and couple-level factors. Finally, based on our pilot, we expect the intervention to have a positive effect on relational outcomes although it is possible that in a larger trial a small subgroup of couples will experience poorer outcomes; identifying characteristics of each common type of couple will allow interpretation of the generalizability of our findings.

**Additional Analyses: Gender as a Moderating Variable:** We will also explore the moderating effect of gender on the effectiveness of *Exercising Together* in couples coping with different cancers (e.g., do women benefit more than men) after controlling for role (i.e., survivor vs spouse/partner). Interaction terms will be added to models described above to test for moderating effects.

**Ancillary study:** Feasibility and acceptability of the ancillary study will be determined by calculating accrual, retention, and adherence rates, number of adverse events, and the proportion of testing visits and surveys completed. Feasibility and acceptability metrics will be compared to those of the parent trial.

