Interested participants will be screened either by phone or in person using an IRB approved screening script. After initial screening, interested and eligible couples will come to the OHSU Knight Cancer Research Building and will be presented with an online IRB-approved Consent Form prior to any study-related procedure. The Consent Form will describe the goals of the study, study procedures, confidentiality, risks, benefits, and voluntary nature of the research. After participants view the consent online, and click the box that they have read and agree to participate (indicating that they have signed the consent), they will be sent links and requested to complete REDCap surveys. For the baseline testing session, couples will be asked to provide a fasting blood draw (which may be completed at an appointment separate of the baseline consenting visit but prior to initiation of the intervention), blood pressure, DXA scan, physical tests (PPB, 1RM leg and bench press, standing balance, and 6 minute walk test), and questionnaires. The testing session will take ~2-3 hours per couple, initially, and will be repeated at 3, 6, & 12 months and only take 1-2 hours. Following baseline testing, the Project Director will provide each couple with an envelope that contains their random assignment to a study group in order to retain blinding of the research assistants who conduct testing. Couples will be randomly assigned to 1 of 3 groups: 1) *Exercising Together*, 2) *Separate survivor / spouse/partner group exercise* 3) *Separate survivor / spouse/partner home exercise*. Enrollment will be stratified by cancer type and average couple age (<60 vs. 60-80). Assignment will be in random blocks of 6-9 couples for even enrollment.

During periods of hospital recommendations for decreased in-person contact, re-consent for the modified procedures will be done over the phone or via teleconference. Study team members will inform the participants of the modified procedures and note their verbal agreement to continue on the study.

Individuals who have not previously consented will be screened by phone or teleconference using an IRB approved screening script. After initial screening, interested and eligible couples will

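### Cancer type, a stratification factor, appears in no Aim 1–3 efficacy model, and age is optional and undefined: a minor efficiency and pre-specification gap

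*Combined protocol and SAP*

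**What the plan says.** - **Randomisation (Section 8.0, Screening tests and procedures).** "Enrollment will be stratified by cancer type and average couple age (<60 vs. 60-80"). With three cancer types and two age bands this gives six strata.
- **Sample size (Section 13.0, Power and Sample Size).** The text plans equal numbers per disease site and says it will "stratify by cancer type at randomization". It does not repeat the age factor.
- **Aim 1 model (Section 13.0, Analysis Plan).** "The Level 1 model has four coefficients representing intercepts (baseline assessments) and slopes (rates of change) for survivors and spouses/partners". At the next level, "Aim 1 will be addressed with Level-2 models that include dummy variables to directly examine the effects of the partnered intervention" against each comparator. Aim 2 reuses this model and Aim 3 builds on the same trajectories.
- **Covariates (Section 13.0, Analysis Plan).** The one general statement is "Age, comorbidities and time since diagnosis will be considered as covariates in all analyses". It does not say whose age is meant, whether age is continuous or banded, or whether covariates enter the intercepts, the slopes or both.
- **Shape of change.** "Models with linear and quadratic change across time will be compared to determine best fit to the data".
- **Additional Analyses.** Different cancers are mentioned in an exploratory analysis of gender as a moderator, but cancer type is not given there as a model term.

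**The concern.** The trial takes the trouble to balance the arms on two factors, and the analysis as written commits to neither. Stratification makes the treatment comparison more precise when the factor predicts the outcome, but a model that omits the factor does not credit that precision. Its standard error still includes the between-type variation that the allocation has removed from the arm comparison. Confidence intervals are then somewhat too wide and some power goes unused.

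For this trial only differences between cancer types in the rate of change matter. Differences in starting level are absorbed by the intercepts.

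The second stake is pre-specification. Covariates that are merely considered, one of them undefined, leave the adjusted model open to choice after the data are seen. That applies to every analysis, including those of the five listed primary outcomes.

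**Working it through.** **1. The plan's own figures.** Inflating 264 couples for 10% attrition gives 264/0.90 = 293.3, so 294, which agrees with the plan. The statement that "264 couples measured 4 times over a 12-month period has a power of 0.80" cannot be reproduced strictly, because alpha and the variance components are not given. As a benchmark, a two-sided 5% comparison of 88 versus 88 couples (264/3) at d = 0.40 has power 0.756, and an omnibus F test with arm means 0.4, 0, 0 has 0.784. To credit the plan's figure, I take 0.80 as the starting point when cancer type explains nothing.

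**2. Set-up.** Two-sided alpha 0.05 (assumed), 88 couples per arm, normal approximation, one pairwise contrast on change.
- Reported standard error without cancer type: √(2/88) = 0.1508 SD of estimated change.
- Effect giving power 0.80: (1.960 + 0.842) × 0.1508 = 0.422 SD.
- R² is the share of variance in estimated change explained by cancer type beyond covariates already fitted. It is assumed.
- True standard error under stratified allocation: √(2(1 − R²)/88).
- Power without the term: Φ[(2.802 − 1.960)/√(1 − R²)].
- Power with the term: Φ[2.802/√(1 − R²) − 1.960].
- Type I error without the term: 2[1 − Φ(1.960/√(1 − R²))].

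**3. Results.**

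| Assumed R² | Power without | Power with | Gain (points) | Type I error without |
|---|---|---|---|---|
| 0 | 0.800 | 0.800 | 0 | 0.050 |
| 1% | 0.801 | 0.804 | 0.3 | 0.049 |
| 5% | 0.806 | 0.820 | 1.4 | 0.044 |
| 10% (upper check) | 0.812 | 0.840 | 2.7 | 0.039 |

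The formulas ignore the degrees of freedom spent. In the most pessimistic accounting (three extra terms, residual degrees of freedom 261 to 258), the standard error at R² = 1% is multiplied by √(0.99 × 261/258) = 1.001, so nothing is gained there.

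**4. Simulation.** 20,000 trials of 264 couples, six equal strata, random blocks of 6 and 9, couple age fitted in both models. At R² = 1%, power was 0.796 without and 0.799 with cancer type, and type I error 4.8% and 4.9%. At R² = 5%, power was 0.802 and 0.818, and type I error 4.5% and 4.9%. Monte Carlo errors are about 0.3 points for power and 0.15 for type I error.

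**5. Parameter cost.** The plan states: "Even in the most complicated model, the proposed sample of 264 couples would exceed the minimum standard of 5-10 subjects per parameter estimated". Assume an intercept, two arm dummies and three covariates in every equation, four random effects (10 variances and covariances) and one residual variance.
- Linear: 4 × 6 + 10 + 1 = 35. Cancer type adds 2 × 4 = 8, giving 43. Couples per parameter go from 264/35 = 7.5 to 264/43 = 6.1.
- Quadratic, cancer type on intercepts and linear slopes only: 6 × 6 + 10 + 1 = 47, plus 8 = 55. Couples: 264/55 = 4.8. Persons: 528/55 = 9.6.
- Quadratic, cancer type on all six equations: 47 + 12 = 59. Couples: 264/59 = 4.5. Persons: 528/59 = 8.9.

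**6. Gender models.** If all breast survivors are female and half of colorectal survivors are male (assumed), the proportions male are 1, 0 and 0.5. The between-type variance is (0.25 + 0.25 + 0)/3 = 0.167 against a total of 0.25, so cancer type explains 0.667 of survivor gender. The variance inflation is 1/(1 − 0.667) = 3.

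**The case against.** The best case against acting is that nothing in the trial's conclusions is shown to change. The gain is about a point or less over most of the assumed range, R² comes from no source in the documents, and the calculation is for one pairwise contrast. The plan's rule requires both a significant group coefficient and a better-fitting model. All of this stands. It sets the priority at minor but does not remove the mismatch between how couples are randomised and how they are analysed.

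Four stronger readings are tempting, and the documents do not support them.
- **That leaving out a stratification factor biases the effect or inflates false positives.** The direction is the opposite: type I error falls to 0.049 at R² = 1% and 0.044 at 5%.
- **That both factors would add precision.** Age is already on the covariate list, so only cancer type can be credited with a gain. For age the issue is definition and commitment.
- **That adding cancer type breaks the plan's rule on subjects per parameter.** The 4.8 depends on counting couples and on the assumed covariates and covariance structure. The rule speaks of subjects, and per person the ratio is 9.6. The plan does not settle which count applies.
- **That individual age must give way to the two-band stratum.** In a model with separate survivor and partner equations, each member's own age is a natural reading, and banding may discard information. No calculation here favours the band.

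**Conclusion.** The gap is real and minor. Cancer type is a randomisation factor and is named in no Aim 1–3 efficacy model; age is named without definition or commitment. Validity is not affected. Where cancer type predicts rate of change, the planned tests are mildly conservative. The power forgone is 0.3 to 1.4 points for R² of 1% to 5%, and effectively nil at 1% or below once degrees of freedom are counted.

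These sizes rest on an assumed R², an assumed two-sided 5% alpha, equal arms, and the plan's 0.80 taken as given. The uncertainty about that 0.80 does not alter the point. The pre-specification argument does not depend on R² and is the steadier reason to amend the text.

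**What to change.** In the Analysis Plan (Section 13.0):
- Pre-specify cancer type (three levels) as a fixed Level-2 covariate on the intercepts and linear slopes of the Aim 1–3 models. Placing it on the intercepts alone would recover little.
- State that age will be fitted, and define it so that it reflects the randomisation factor, for example as continuous couple mean age, in place of the undefined term and not in addition to it.
- If the quadratic model is kept, leave cancer type off the quadratic terms, and say whether the subjects-per-parameter rule counts couples or persons.
- Name both stratification factors in Power and Sample Size.
- Treat the exploratory gender models separately and say whether cancer type stays in them, given its overlap with survivor gender.

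The cost is SAP wording. Age and cancer type are already collected at baseline (Section 3.0, Descriptive Measures). The statistical price is about 8 extra fixed parameters in the linear model. No visit, procedure or sample size changes.
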